9.4 Renal safety monitoring

Renal events are defined as one of the following:

- confirmed (after ≥ 24h) increase in serum creatinine of ≥ 25% compared to baseline during normal hydration status
- new onset (≥1+) proteinuria, hematuria or glucosuria; or as a
- doubling in the urinary albumin-creatinine ratio (ACR) or urinary protein-creatinine ratio (PCR) (if applicable).

The following two categories of abnormalities/adverse events have to be considered during the course of the study:

- Serum creatinine triggers that will require follow up and repeat assessments of the abnormal laboratory parameter
- Urine dipstick triggers that will require follow up and repeat assessments of the abnormal laboratory parameter

Table 9-3 Specific renal alert criteria and actions

Renal Event	Actions
Serum creatinine increase 25 – 49% compared to baseline	Confirm 25% increase after 24-48h Follow up within 2-5 days
Serum creatinine increase \geq 50 % compared to baseline	Follow up within 24-48h if possible Consider drug interruption Consider patient hospitalization /specialized treatment
Albumin- or Protein-creatinine ratio increase \geq 2-fold	Confirm value after 24-48h Perform urine microscopy
Albumin-creatinine ratio (ACR) \geq 30 mg/g or \geq 3 mg/mmol; New dipstick proteinuria \geq 1+ Protein-creatinine ratio (PCR) \geq 150 mg/g or >15 mg/mmol	Consider drug interruption / discontinuation
New dipstick glucosuria \geq 1+ not due to diabetes	Blood glucose (fasting) Perform serum creatinine, ACR
New dipstick hematuria not due to trauma	Urine sediment microscopy Perform serum creatinine, ACR
Document contributing factors: co-medication, other co-morbid conditions, and additional diagnostic procedures performed in the CRF	
Monitor patient regularly (frequency at investigator's discretion) until one of the following: Event resolution: (sCr within 10% of baseline or protein-creatinine ratio within 50% of baseline) Event stabilization: sCr level with $\pm 10\%$ variability over last 6 months or protein-creatinine ratio stabilization at a new level with $\pm 50\%$ variability over last 6 months.	

9.5 Pregnancy reporting

To ensure patient safety, each pregnancy in a patient on study drug must be reported to Novartis within 24 hours of learning of its occurrence. The pregnancy should be followed up to determine outcome, including spontaneous or voluntary termination, details of the birth, and the presence or absence of any birth defects, congenital abnormalities, or maternal and/or newborn complications. The study drug must be discontinued, though the patient may stay in the study, if she wishes to do so. All assessments that are considered as a risk during pregnancy must not be performed. The patient may continue all other protocol assessments. Pregnancy must be recorded on a Pharmacovigilance Pregnancy Form and reported by the investigator to the local Novartis Drug Safety and Epidemiology Department. Pregnancy follow-up should be recorded on the same form and should include an assessment of the possible relationship to the Novartis study drug of any pregnancy outcome. Any SAE experienced during pregnancy must be reported on an SAE Report Form.

Pregnancy outcomes must be collected for the female partners of any males who took study treatment in this study. Consent to report information regarding these pregnancy outcomes should be obtained from the mother.

All SAEs relating to suicidal behavior should be reviewed by the Safety Management Team or Early Project Teams.

9.6 Early phase safety monitoring

The Investigator will monitor adverse events in an ongoing manner and inform the Sponsor of any clinically relevant observations. Any required safety reviews will be made jointly between medically qualified personnel representing the Sponsor and Investigator. Such evaluations may occur verbally, but the outcome and key discussion points will be summarized in writing (e-mail) and made available to both Sponsor and all Investigator(s). Criteria pertaining to stopping the study/treatment or adapting the study design are presented above.

When two or more clinical site(s) are participating in the clinical study, the Sponsor will advise the Investigator(s) at all sites in writing (e-mail) (and by telephone if possible) of any new, clinically relevant safety information reported from another site during the conduct of the study in a timely manner.

10 Data review and database management

10.1 Site monitoring

Before study initiation, at a site initiation visit or at an investigator's meeting, a Novartis representative will review the protocol and CRFs with the investigators and their staff. During the study, Novartis employs several methods of ensuring protocol and GCP compliance and the quality/integrity of the sites' data. The monitor will visit the site to check the completeness of patient records, the accuracy of entries on the CRFs, the adherence to the protocol and to Good Clinical Practice, the progress of enrollment, and to ensure that study drug is being stored, dispensed, and accounted for according to specifications. Key study personnel must be available to assist the monitor during these visits.

The investigator must maintain source documents for each patient in the study, consisting of case and visit notes (hospital or clinic medical records) containing demographic and medical information, laboratory data, electrocardiograms, and the results of any other tests or assessments. All information on CRFs must be traceable to these source documents in the patient's file. The investigator must also keep the original informed consent form signed by the patient (a signed copy is given to the patient).

The investigator must give the monitor access to all relevant source documents to confirm their consistency with the CRF entries. Novartis monitoring standards require full verification for the presence of informed consent, adherence to the eligibility criteria, documentation of SAEs, and the recording of data that will be used for all primary and safety variables. Additional checks of the consistency of the source data with the CRFs are performed according to the study-specific monitoring plan. No information in source documents about the identity of the patients will be disclosed.

10.2 Data collection

Designated investigator staff will enter the data required by the protocol into the Electronic Case Report Forms using fully validated software that conforms to 21 CFR Part 11 requirements. Designated investigator site staff will not be given access to the EDC system until they have been trained. Automatic validation programs check for data discrepancies and, by generating appropriate error messages, allow the data to be confirmed or corrected before transfer of the data to the CRO working on behalf of Novartis. The Investigator must certify that the data entered into the Electronic Case Report Forms are complete and accurate. After database lock, the investigator will receive a CD-ROM or paper copies of the patient data for archiving at the investigational site.

Data not requiring a separate written record will be defined in the Site Operations Manual and assessment schedule and can be recorded directly on the CRFs. All other data captured for this study will have an external originating source (either written or electronic) with the CRF not being considered as source.

All data should be recorded, handled and stored in a way that allows its accurate reporting, interpretation and verification.

CRO working on behalf of Novartis review the data entered into the eCRFs by investigational staff for completeness and accuracy and instruct the site personnel to make any required corrections or additions. Queries are sent to the investigational site using an electronic data query. Designated investigator site staff is required to respond to the query and confirm or correct the data. If the electronic query system is not used, a paper Data Query Form will be faxed to the site. Site personnel will complete and sign the faxed copy and fax it back to CRO working on behalf of Novartis who will make the correction to the database.

Concomitant medications entered into the database will be coded using the WHO Drug Reference List, which employs the Anatomical Therapeutic Chemical classification system. Medical history/current medical conditions and adverse events will be coded using the Medical dictionary for regulatory activities (MedDRA) terminology.

Laboratory samples will be processed centrally and the results will be sent electronically to Novartis (or a designated CRO).

Corporate Confidential Information

10.3 Data Monitoring Committee

Not required.

10.4 Adjudication Committee

Not required.

11 Data analysis

11.1 Analysis sets

For all analysis sets, patients will be analyzed according to the study treatment(s) received.

The safety analysis set will include all patients that received any study drug.

Corporate Confidential Information

11.2 Subject demographics and other baseline characteristics

All data for background and demographic variables will be listed by patient. Summary statistics will be provided.

Relevant medical history, current medical conditions, results of laboratory screens, drug tests and any other relevant information will be listed by patient.

11.3 Treatments (study drug, rescue medication, other concomitant therapies, compliance)

Data for study drug administration (rescue medication) and concomitant therapies will be listed by patient.

11.4 Analysis of the primary variable(s)

The primary aim of this study is to assess the effects of CFZ533 on thyroid function, focusing on TSH levels, total T3 and free T4 in GD after 12 weeks of treatment.

11.4.1 Variable(s)

The effects of CFZ533 on thyroid function will be primarily assessed by the proportion of patients whose TSH levels normalize (above 0.35 mU/L) after 12 weeks of treatment. They will also be assessed by the difference in mean total T3 and free T4 between baseline and after 12 weeks of treatment.

11.4.2 Statistical model, hypothesis, and method of analysis

One of the main efficacy criteria for this study is to show that the proportion of patients with normalization of TSH (above 0.35 mU/L) after 12 weeks of treatment with CFZ533 is statistically greater than 5%, according to a 1-sided exact test for proportions with a 10% type I error. This will be achieved if we observe at least 3/12 responders since in that case the lower bound of an 80% confidence interval for the proportion of responders will be about 10%. The other efficacy criteria are that there is a significant reduction in average total T3 and free T4 after 12 weeks of treatment, according to a 1-sided paired t-test with 10% type I error for each of these two endpoints.

11.4.3 Handling of missing values/censoring/discontinuations

Patients who discontinue after the 4 week efficacy assessment for any reason will be considered non-responders in the primary analysis (unless their last recorded TSH value was after 8 weeks of treatment and was above the lower limit of the normal range, 0.35 mU/L). Patients who discontinue before 4 weeks of treatment for any reason will be replaced and not counted for the calculation of responders. For total T3 and free T4, the last recorded value will be used for the change from baseline, provided it was obtained after at least 8 weeks of treatment.

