7.1 Discontinuation of study treatment

Patients may voluntarily discontinue study treatment for any reason at any time.

The investigator **must** discontinue study treatment for a given patient if, on balance, he/she believes that continuation would be detrimental to the patient's well-being.

Study treatment **must** be discontinued under the following circumstances:

- Patient withdraws consent
- Pregnancy
- Grade 3 or higher allergic reaction
- Acute, Grade 3 or higher infection as judged by the Investigator

The study treatment should be discontinued if:

- Clinically significant worsening of Graves' disease, eg. beta-blocker unable to control the symptoms of hyperthyroidism, at the discretion of the Investigator.
- New onset atrial fibrillation or angina.
- On balance, the investigator believes that continuation would be detrimental to the patient's well-being.

Discontinuation of study treatment will be at the discretion of the Investigator, under the following circumstances:

- Use of prohibited treatment as per [Section 5.2](#).
- Any other protocol deviation that results in a significant risk to the patient's safety

Patients who discontinue study treatment or who decide they do not wish to participate in the study further should NOT be considered withdrawn from the study UNLESS they withdraw their consent (see [Section 7.3](#)). Where possible, they should return for the assessments defined in the [Assessment table](#). If they fail to return for these assessments for unknown reasons, every effort (e.g. telephone, e-mail, letter) should be made to contact them as specified in [Section 7.2.1](#). Patients who discontinue the drug before having completed 4 weeks of treatment and 4 week efficacy and safety evaluations will be replaced with a newly enrolled patient.

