11.6 Sample size calculation

The proposed sample size for this study is 12 patients (to complete the study). Assuming CFZ533 is associated with 38% normalization of the TSH levels after 12 weeks of treatment (which is consistent with the response rate seen with Rituximab in 26 weeks in one small, open-label study ([Heemstra et al 2008](#)), there is around 89% power to detect a proportion of TSH responders significantly higher than 5% (this would be achieved with at least 3/12 responders), with a type I error of 10%. Additionally, this sample size provides 98% power to detect normalization of the total T3 (and free T4, respectively) below the upper limit of the normal range (2.79 nmol/L and 22.7 pmol/L, respectively). The assumed baseline levels are 7.2 nmol/L for total T3 and 58.55 pmol/L for free T4, which are the average values reported in GD patients in [Andrade et al \(2001\)](#). The assumed standard deviation for the change from baseline are 4.24 nmol/L and 34.58 pmol/L respectively.

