	No study drug taken	Yes
Subjects are excluded from PD analysis in case of these PDs:		
I01	Deviation from inclusion criteria 1 (ICF not obtained)	Yes
	No study drug taken	Yes

Category Deviation code	Text description of deviation	Data exclusion
	Subject took any prohibited medications interfering with efficacy	Yes
Subjects are excluded from PK and PD analysis in case of these PDs:		Exclude subject from PK and PD analysis sets
I01	Deviation from inclusion criteria 1 (ICF not obtained)	Yes
	No study drug taken	Yes

There are two categories of medications which are considered rescue medication. In order to identify these for programming purposes these are included in the protocol deviations dataset with codes of O01 and O02 (oral corticosteroids and anti-thyroid drugs) however they are not protocol deviations so will not be included in the protocol deviations listing, instead they will be included in a separate rescue medication listing.

In PD outputs the following rules will be applied to subjects who received rescue medication

- Data post rescue medication will be flagged in the listings with a * and a footnote added to explain.
- Figures showing individual profiles will appear as red lines from the point at which the rescue medication was taken and a footnote added to explain.
- In summary tables and summary figures datapoints after rescue medication will be excluded and a footnote added to explain.
- In the inferential analyses datapoints after rescue medication will be excluded and a footnote added to explain. For the longitudinal models the model is expected to provide unbiased results under the assumption that the rescue medication intake can be considered dependent only on previously observed values (MAR – missing at random).

If updates to this table are needed, an amendment to the SAP needs to be implemented prior to DBL.

5 Statistical methods for Pharmacokinetic (PK) parameters

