6.1.3.1 Handling of missing values/censoring/discontinuations

Patients who discontinue after the 4 week efficacy assessment for any reason will be considered non-responders in the primary analysis (unless their last recorded TSH value was after 8 weeks of treatment and was above the lower limit of the normal range, 0.35 mU/L). Patients who discontinue before 4 weeks of treatment for any reason will be replaced and not counted for the calculation of responders. For total T3 and free T4, the last recorded value will be used for the change from baseline (Day 1, predose), provided it was obtained after at least 8 weeks of treatment.

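### The week-8 exception to the non-responder rule is not limited by reason for stopping or by rescue, so a patient who worsens before Day 85 can be scored a week-12 TSH responder

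*Protocol*

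**What the plan says.** The primary responder criterion (Protocol 11.4.2, SAP 6.1.3) is that the proportion with TSH above 0.35 mU/L after 12 weeks "is statistically greater than 5%, according to a 1-sided exact test for proportions with a 10% type I error". The decision rule is stated directly: "This will be achieved if we observe at least 3/12 responders".

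The missing-data rule is the same in Protocol 11.4.3 and SAP 6.1.3.1. The default is strict: "Patients who discontinue after the 4 week efficacy assessment for any reason will be considered non-responders in the primary analysis". It is then lifted "unless their last recorded TSH value was after 8 weeks of treatment and was above the lower limit of the normal range, 0.35 mU/L". The exception has two conditions, the timing and the level of the last TSH. The reason for stopping and the use of rescue are not mentioned. For total T3 and free T4, the last value from at least week 8 onward is used in the change from baseline.

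Three other provisions bear on this:

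- Protocol 7.1 lists among the grounds for stopping study treatment: "Clinically significant worsening of Graves' disease, eg. beta-blocker unable to control the symptoms of hyperthyroidism, at the discretion of the Investigator". Protocol 6.9 allows standard-of-care treatment on worsening and says the patient is then discontinued from the study.
- SAP Section 4 treats oral corticosteroids and anti-thyroid drugs as rescue, and says: "In the inferential analyses datapoints after rescue medication will be excluded and a footnote added to explain". Its missing-at-random argument covers the longitudinal models only. It does not say how a rescued patient is scored in the responder test.
- The visit schedule (Protocol 3.1, Table 8-1) has Day 57 and Day 85, with nothing scheduled between them.

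**The concern.** The default treats any dropout after week 4 as a failure, which is the cautious choice in a study without a control arm. The exception is reasonable for a patient who leaves for unrelated reasons while TSH is normal. As written, it also reaches a patient who leaves because the disease has worsened. For that patient the Day 57 value predates the failure, yet it can stand as evidence of normalisation at week 12.

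The SAP rescue rule adds to this. If post-rescue values are removed and rescue is not itself an outcome, the last remaining value can be the favourable one taken before rescue. In the responder test the exception can only move a patient from non-responder to responder, so any error favours CFZ533. The week-12 paired t-tests on total T3 and free T4 can take in pre-worsening Day 57 values by the same route.

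**Working it through.** **Inputs.** From Protocol 11.4.2 and 11.6: n = 12, null rate 5%, one-sided exact test at 10%, success at 3 or more responders, assumed true rate 38%, stated power about 89%. From Protocol 3.2: under 1% of placebo-treated patients predicted to rise above 0.3 mU/L within 12 weeks by random variability. The documents give no rate of worsening or rescue between Day 57 and Day 85.

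**Plan's own figures.** With X binomial(12, p):

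- P(X ≥ 3 | 0.05) = 1 − (0.5404 + 0.3413 + 0.0988) = 0.0196, the actual type I error.
- P(X ≥ 2 | 0.05) = 1 − (0.5404 + 0.3413) = 0.118, so 3 is the smallest valid threshold.
- P(X ≥ 3 | 0.38) = 0.893, matching the stated 89%.
- The exact 80% lower bound at 3/12 is 9.6%, matching the stated value of about 10%.

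The design figures reproduce. The issue is only how individual patients are scored.

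**The rule applied to three illustrative records**, each with Day 57 TSH of 0.40 mU/L:

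- A. Moves away on Day 70. Responder, plausibly as intended.
- B. Stopped on Day 70 for worsening, not rescued. If a Day 85 or exit TSH is obtained, that value decides. If not, Day 57 is the last value: responder.
- C. Given an anti-thyroid drug on Day 70, attends Day 85. If SAP Section 4 removes the Day 85 value before the last value is chosen, Day 57 remains: responder.

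**Conditions needed for B or C to be misclassified:**

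1. Day 57 TSH is above 0.35 mU/L.
2. There is no later usable pre-rescue TSH.
3. For C, the last recorded value is read as the last usable value, and the patient stays in the PD analysis set.
4. Day 57 counts as after 8 weeks. It is exactly 56 days after Day 1. The parallel T3/T4 sentence says at least 8 weeks, and otherwise no scheduled sample before Day 85 could trigger the exception.

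**Effect of one patient.** Moving from 2/12 to 3/12 adds 1/12 = 8.3 points and takes p from 0.118 to 0.0196. If one of the 12 is a responder only through the exception and the other 11 have a true 5% rate, P(success) = P(X ≥ 2 of 11) = 0.102.

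**Effect of a rate.** Let q, an assumption, be the share added to the 5% null rate by such cases. P(X ≥ 3 of 12) at 5% + q:

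| q | P(success) |
|---|---|
| 0 | 0.020 |
| 1% | 0.032 |
| 2.5% | 0.056 |
| 5% | 0.111 |

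The probability reaches 0.10 at a scored rate of 9.57%, that is q of about 4.6 points. Dropouts after week 4 stay in the denominator, so up to about 15 patients may be scored. With 15 the threshold is still 3 (2/15 gives p = 0.171), and the corresponding values are 0.036, 0.057, 0.097 and 0.184.

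**The case against.** A reader might infer that every patient stopped or rescued for worsening after Day 57 is scored a responder. The documents do not support that. The rule uses the last TSH. Protocol 7.1 asks patients who stop treatment to keep attending where possible, and Protocol 3.1 asks those who leave the study to complete the end-of-study assessments, which include TSH. A low value drawn before rescue makes the patient a non-responder. For a rescued patient the outcome also depends on joining two provisions that the SAP does not join: the exclusion of post-rescue data and the choice of last value. It depends on analysis-set membership too. Methimazole and propylthiouracil are prohibited in Protocol Table 5-1, and SAP Table 4-1 removes from the PD analysis anyone who took prohibited medication interfering with efficacy. The SAP text nevertheless says anti-thyroid drugs given as rescue are not protocol deviations. All of this stands, and it is why the point says such a patient can be scored a responder.

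A reader might also infer that the 10% error level is breached. That needs q of about 4.6 points at n = 12. Under an inactive drug, q cannot exceed the share normalised by chance at Day 57, which on the premise of Protocol 3.2 is under 1%. A larger q would need something else, such as transient drug responses.

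The SAP gives some visibility: rescue listings, flagged post-rescue values, profiles split by rescue status, and a repeated-measures model for T3 and T4. None of these changes the responder count in the primary test. The sensitivity analysis in Protocol 11.4.4 and SAP 6.1.3.2 is optional, unspecified and considered only after more than two discontinuations, whereas one patient can decide the result.

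Finally, counting worsening as failure adds an investigator-judged component to a laboratory endpoint chosen for its objectivity, in an open-label study. That is a real cost. It is, however, consistent with the plan's own default, which already counts discontinuation for any reason as failure.

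**Conclusion.** The point holds as a gap in the scoring rule. Neither document limits the week-8 exception by reason or by rescue, and the SAP excludes post-rescue data without giving rescue an outcome in the responder test. A patient who meets the conditions listed above can be counted as a week-12 TSH responder after treatment has failed.

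The expected effect is small: from 2.0% to at most about 3.2% false success with 12 patients, given the protocol's premise on chance normalisation. The frequency is unknown and probably low. The effect on a close result is decisive, because one patient separates failure at 2/12 from success at 3/12, and the direction always favours CFZ533. The effect on the T3 and free T4 t-tests cannot be sized from the documents.

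The stated threshold, sample size and power are not in error.

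**What to change.** In Protocol 11.4.3 and SAP 6.1.3.1, state that for the TSH responder analysis the week-8 exception does not apply to patients who, before the Day 85 sample, (i) discontinued for worsening of Graves' disease, (ii) received rescue medication as categorised in SAP Section 4 (oral corticosteroids, anti-thyroid drugs), or (iii) received other standard-of-care treatment for Graves' hyperthyroidism. These patients count as non-responders and stay in the denominator.

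Reconcile Protocol Table 5-1 and SAP Table 4-1 with the SAP text that rescue drugs are not protocol deviations, so that membership of the PD analysis set is settled before database lock. Exclusion would not be neutral. Two responders among 12 give p = 0.118, but if two rescued non-responders are removed, 2/10 gives p = 1 − (0.5987 + 0.3151) = 0.086, a success.

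List every patient classed by the exception with the reason for stopping, and show in the same listing whose Day 57 T3 and T4 were carried forward. Pre-specify a sensitivity analysis without the exception.

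**Cost.** A few sentences in each document. Rescue use is already recorded under Protocol 6.9. The sponsor should confirm that the reason for stopping is captured too, since the protocol explicitly asks for it only at withdrawal of consent (7.3). The threshold, type I error (0.0196) and power at 38% (0.893) do not change. The observed responder rate may be slightly lower. If a share f of the assumed 38% had consisted of such patients (f is an assumption), power would be 0.866 at f = 5%, 0.835 at 10% and 0.757 at 20%. The endpoint also takes in a judgement by the investigator, which the listing and the sensitivity analysis make visible.

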11.4.4 Supportive analyses

In case more than 2 discontinuations occur in this study, additional methods may be used to assess sensitivity of the results to different imputation techniques to deal with the missing data.

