1.4 Study design and treatment

This is a non-confirmatory, open-label, one treatment arm study in patients with newly diagnosed GD.

A total of approximately 15 patients will be enrolled and treated with CFZ533 to ensure approximately 12 completers. For each patient, the study will consist of a screening epoch of up to 28 days, a baseline evaluation, a 12-week treatment epoch, 24-week follow up epoch after the last dosing of CFZ533 on Study Day 85, and a study completion evaluation on Study Day 253. Patients who discontinue the drug before having completed 4 weeks of treatment and 4 week efficacy and safety evaluations will be replaced with a newly enrolled patient. The study design is presented in Figure 1-1.

Figure 1-1 Study design

2 First interpretable results (FIR)

First interpretable results (FIR) will be provided for this trial.

The study FIR template (mock slides) can be found in CREDI in the study RAP folder.

The template shows the analysis / results to be presented in the FIR. Study outputs required to be created at the time of the FIR will be highlighted in TFL shells document and marked as "Key" in the Programming Deliverables Tracker (PDT) output list.

3 Interim analyses

Corporate Confidential Information

4 Statistical methods: Analysis sets

For all analysis sets, patients will be analyzed according to the study treatment received.

All patients that received study drug and with no protocol deviations with relevant impact on safety will be included in the safety analysis set.

The PK analysis set will include all patients with at least one available valid (i.e. not flagged for exclusion) PK concentration measurement, who received any study drug and experienced no protocol deviations with relevant impact on PK data.

The PD analysis set will include all patients with any available PD data, who received any study drug and experienced no protocol deviations with relevant impact on PD data, who have completed at least 4 weeks of treatment with CFZ533.

The analysis sets and protocol deviation codes are related as follows:

Table 4-1 Protocol deviation codes and analysis sets

Category Deviation code	Text description of deviation	Data exclusion
Subjects are excluded from all (safety) analysis in case of these PDs:		
I01	Deviation from inclusion criteria 1 (ICF not obtained)	Yes
	No study drug taken	Yes
Subjects are excluded from PK analysis in case of these PDs:		
I01	Deviation from inclusion criteria 1 (ICF not obtained)	Yes

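### Patients who stop before week 4 are left out of the TSH responder rate, and no readable section plans a rate in all treated patients

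*Protocol*

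**What the plan says.** The rule for early stoppers is in Protocol 11.4.3 and, in the same words, in SAP 6.1.3.1: "Patients who discontinue before 4 weeks of treatment for any reason will be replaced and not counted for the calculation of responders". The PD analysis set in SAP Section 4 adds its own condition, taking only patients "who have completed at least 4 weeks of treatment with CFZ533".

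Later stoppers are handled differently. Protocol 11.4.3 says: "Patients who discontinue after the 4 week efficacy assessment for any reason will be considered non-responders in the primary analysis". The exception is a patient whose last TSH came after week 8 and was above 0.35 mU/L.

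Protocol 7.1 lists reasons for stopping treatment that can arise at any time. They include a severe allergic reaction, a severe infection, and worsening disease such as "beta-blocker unable to control the symptoms of hyperthyroidism". It also says that patients who stop treatment "should NOT be considered withdrawn from the study UNLESS they withdraw their consent", and asks that they return for assessments where possible. For patients who take rescue, SAP Section 4 states: "In the inferential analyses datapoints after rescue medication will be excluded".

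The only sensitivity provision that could reach the TSH rate is in Protocol 11.4.4 and SAP 6.1.3.2. If there are more than 2 discontinuations, "additional methods may be used to assess sensitivity of the results to different imputation techniques". The repeated measures model in SAP 6.1.3.2 covers T3 and T4, not TSH response.

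Protocol 11.1 defines a set of all treated patients: "The safety analysis set will include all patients that received any study drug". No readable section attaches a responder rate to it. SAP Section 4 defines the safety set more narrowly, removing patients with protocol deviations that bear on safety.

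**The concern.** Membership of the denominator depends on something that happens after treatment starts. A patient who stops at week 3 for worsening disease disappears from the responder calculation, whereas one who stops at week 5 for the same reason counts as a failure. No readable passage explains the difference. Some early stops may reflect lack of effect or intolerance, so leaving them out can make the drug look better than it did across everyone who received it.

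The TSH responder rate is the leading efficacy measure in a single-arm trial whose purpose is to decide whether further development is warranted. If anyone stops early, the planned rate and interval describe only patients who lasted 4 weeks, and no planned figure covers the rest. The sensitivity provision does not fill the gap. It is optional, one or two discontinuations would not trigger it, and it concerns imputation, not who is in the denominator.

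**Working it through.** **Inputs.** Null rate 5%, one-sided exact test at 10%, success at 3 or more of 12 (Protocol 11.4.2). Assumed response 38%, stated power about 89% (Protocol 11.6). About 15 enrolled for about 12 completers (Protocol 3.1). The number of early stoppers, k, is not given. I take k = 1 to 3 as an assumption; k = 3 puts the whole gap between 15 and 12 into the first 4 weeks.

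**Reproducing the plan's figures** (X is the number of responders)
- Power: P(X ≥ 3 | 12, 0.38) = 0.893, which agrees with the stated 89%.
- Type I error: P(X ≥ 3 | 12, 0.05) = 0.0196. A cut-off of 2 gives 0.118, above 0.10, so 3 is correct for 12 patients.
- Clopper-Pearson 80% interval for 3/12: 9.6% to 47.5%, which agrees with the stated lower bound of about 10%.

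**Effect on the estimate.** With x responders among n counted and k early stoppers scored as non-responders, the reported rate is x/n and the all-treated rate is x/(n+k). Their ratio is (n+k)/n. For n = 12 and x = 3:

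| k | All-treated rate | 80% CI | Factor (12+k)/12 |
|---|---|---|---|
| 0 | 3/12 = 25.0% | 9.6% to 47.5% | 1.00 |
| 1 | 3/13 = 23.1% | 8.8% to 44.4% | 1.08 |
| 2 | 3/14 = 21.4% | 8.1% to 41.7% | 1.17 |
| 3 | 3/15 = 20.0% | 7.6% to 39.3% | 1.25 |

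If the rate among the 12 counted equals the design value of 38%, the all-treated rate is 0.38 × 12/(12+k) = 35.1%, 32.6% or 30.4%.

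**The factor depends on n.** Later stoppers are counted, so n need not be 12.
- If the 15 enrolled include the early stoppers, n = 15 − k and the factor is 15/(15−k) = 1.07, 1.15 or 1.25.
- If replacements come on top of 15, n = 15 and the factor is (15+k)/15 = 1.07, 1.13 or 1.20.

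**The direction depends on the scoring.** If one early stopper stays in follow-up without rescue and is scored on an observed week-12 TSH above 0.35 mU/L, 3/12 becomes 4/13 = 30.8% (14.2% to 52.3%), which is higher than 25.0%.

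**Cut-off, power and type I error**
- With 12 counted, the cut-off and power are as planned. If the all-treated rate is 5% and the k early stoppers are non-responders, the rate among the 12 is 0.05 × (12+k)/12, and P(X ≥ 3) = 0.024, 0.029 or 0.035 for k = 1, 2 or 3. All are below 0.10.
- With 11 counted, P(X ≥ 2 | 11, 0.05) = 0.102, so the cut-off stays at 3. Power falls to P(X ≥ 3 | 11, 0.38) = 0.852.
- With 10 counted, P(X ≥ 2 | 10, 0.05) = 0.086, so the cut-off becomes 2. Two responders would then succeed, although 2 of 12 would fail (0.118).

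**Can fewer than 12 be counted?** The replacement rules disagree:
- The synopsis design row, Protocol 3.1 and 7.1, and SAP 1.4 replace anyone who stops the drug before completing week 4.
- Protocol 11.4.3 and SAP 6.1.3.1 replace early stops for any reason, without saying whether the drug or the study is meant.
- Protocol Section 4 replaces only those who leave the study early for non-safety reasons.
- The synopsis Population row makes replacement optional and excepts patients whom the investigator stops for adverse events.

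If early safety stops are not counted and not replaced, n can be smaller than planned.

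**The case against.** The strongest defence is that this is a disclosed choice. The week-4 rule is the same in both documents, the study is labelled non-confirmatory, and Protocol 3.3 argues that 12 weeks of treatment are needed to test the hypothesis. Not counting patients with under 4 weeks of treatment is a defensible proof-of-concept choice. The effect is small beside an interval about 38 points wide: with 3 responders, the lower bound stays above 5% even at k = 3. A reader who knows the responder count and the number treated can work out the second rate.

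Much of this stands. It is a reason to keep the primary analysis and to call the effect modest. It does not remove the case for a planned second rate: a figure that readers must build themselves is not pre-specified, and its scoring rule would be open to argument afterwards.

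Three stronger readings are tempting and are not supported:
- **The reported rate is always inflated.** It is not. The rates are equal with no early stoppers or no responders, and the 4/13 example reverses the direction. An early stopper who takes rescue cannot reverse it, because later data are excluded.
- **The exclusion breaks the test.** With 12 counted it does not; the type I error stays well below 10%. Nor may one say that cut-off and power are safe in every case, since that requires 12 counted patients.
- **The plan certainly contains no all-treated rate.** Parts of Protocol 11.1 and 11.5 and of SAP 6.2 are redacted. The statement is limited to what can be read, although SAP Section 4 gives the PD set and its 4-week condition in full.

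The added rate also has a weakness. Scoring every early stop as a failure is stricter than the later-stopper rule, which allows an exception for a late normal TSH. It must be presented as a conservative bound.

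**Conclusion.** The concern holds in a limited form. The planned TSH responder rate leaves out everyone who stops before week 4, for reasons that may relate to the outcome, and no readable section plans a rate in all treated patients. If early stoppers are scored as non-responders, the overstatement with 12 counted is a factor of 1.08 to 1.25 for k = 1 to 3. Under the other two readings of the 15 enrolled it is 1.07 to 1.25 or 1.07 to 1.20. These sizes rest on an assumed k and on that scoring. The consequence is for the estimate and its interval, and it is modest. The inconsistent replacement wording is a separate matter that affects n, and through n the cut-off and power. This should be changed, but it does not undermine the primary analysis.

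**What to change.** Keep the primary analysis as it is. Add to Protocol 11.4.4 and SAP 6.1.3.2 a mandatory TSH responder rate with 80% CI in all patients who received any study drug, regardless of protocol deviations and without the 4-week condition. Define this set explicitly in SAP Section 4, because the SAP safety set is narrower than the one in Protocol 11.1. Score stops before week 4 as non-responders, state that this is a conservative bound stricter than the later-stopper rule, and report it beside the planned rate.

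Reconcile the replacement wording in the synopsis, Protocol 3.1, 4, 7.1 and 11.4.3, and SAP 1.4 and 6.1.3.1, so that it is clear who is replaced and how many patients are counted.

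The cost is one extra table and matching text. The second rate may be slightly lower than the planned one, partly because stops unrelated to treatment, and any early stopper whose TSH later normalises, count as failures. Showing both rates makes that visible.
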